### **Inclusion criteria**

- 1) Aged 18-70 year;
- 2) Onset of pancreatitis within 2 weeks;
- 3) Complicated with gastrointestinal failure, which was defined if the patients were complicated with obvious abdominal distention, abdominal rumbling sound weakening or disappearance, no self-defecation as well as intra-abdominal hypertension (IAH).

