### **Sample size**

To detect a minimal clinically relevant difference of 35% between FMT group and control group in the primary outcome, and estimating that FMT would achieve 85% power and control would achieve 50% power and using a type I error of 0.05 and a type II error of 0.20 (80% power), we calculated that a minimal sample size of 48 with 24 patients in each group was required. To allow for dropouts, we included 60 participants with 30 in FMT group and 30 in control group.

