### **Randomization and masking**

A randomization sequence for 60 participants with an allocation ratio of 1:1 was generated using SPSS by an independent statistician who not involved in the clinical performance of the trial. The method of allocation concealment was sequentially numbered sealed opaque envelopes technique. Each participant got a study number at enrolment. An allocator (non-study personnel) then allocated participants to FMT or control group by the randomization sequence. This was done in a closed room and the allocation sequence were immediately disposed of. Investigators, patients and outcome assessors were kept masked to the allocation. The randomization key was revealed to researchers when all participants completed the 6-month follow-up and data analysis was completed.

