### **Secondary endpoints**

The secondary end points were any infectious complication, OF, functional assessments of gut barrier and inflammatory indicators, hospital stay and mortality. Infectious complications included IPN, infected ascites, bacteremia, pneumonia, urinary tract infection. Microbiological data for each of the infectious complications were collected. OF was defined as a score of 2 or more using the modified Marshall scoring system, which was recommended by 2012 Atlanta Classification Creation. Persistent organ failure, that is, organ failure >48 hours. Blood samples were collected from all included patients before and one week after intervention. Gut barrier function was assessed by detecting serum D-Amino Acid Oxidase (DAO) and endotoxin using commercial kits (Cloud-Clone Corp, TX, USA for DAO and ELX800 (Bio Tek) for endotoxin). C-reactive protein (CRP) and procalcitonin (PCT) were measured by IMMAGE 800 (Beckman Coulter) and AFIAS-50 (JOINSTAR) separately. Stools were requested for microbiota analysis at baseline, one week and two week after intervention.

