### **Statistical analysis**

Quantitative variables are presented as medians (ranges) or means  $\pm$  standard deviations and were analysed using the Mann-Whitney U test or t-test as appropriate. Categorical variables are reported as absolute numbers and proportions and were tested by the chi-square test or Fisher's exact test as appropriate. The differences between outcomes for matching data were tested with the paired t test or Wilcoxon signed-rank test as appropriate. We estimated relative risks (RRs) and 95% confidence intervals (CIs) for primary outcomes and secondary outcomes. A two-tailed P value  $<0.05$  was considered statistically significant. Data were analyzed using SPSS software (v17.0; SPSS Inc., Chicago, IL, USA).

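### DAO, endotoxin, CRP and PCT are compared between arms by an unadjusted test that ignores the baseline sample, and the only effect measure with a confidence interval (relative risk) does not fit them

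*Combined protocol and SAP*

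**What the plan says.** The combined protocol and SAP lists the secondary endpoints under Secondary endpoints: "The secondary end points were any infectious complication, OF, functional assessments of gut barrier and inflammatory indicators, hospital stay and mortality". Gut barrier function is measured by serum DAO and endotoxin, and inflammation by CRP and PCT. All four are concentrations, and no cut-off is given for any of them. On sampling it says: "Blood samples were collected from all included patients before and one week after intervention".

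The Statistical analysis section is a single paragraph. Three of its provisions bear on these markers:

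- Quantitative variables are summarised by medians and ranges or by means and "standard deviations and were analysed using the Mann-Whitney U test or t-test as appropriate".
- Before-after comparisons within patients are covered by this sentence: "The differences between outcomes for matching data were tested with the paired t test or Wilcoxon signed-rank test as appropriate".
- The only provision for effect sizes with an interval reads: "We estimated relative risks (RRs) and 95% confidence intervals (CIs) for primary outcomes and secondary outcomes".

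It names no ANCOVA, regression or other between-arm method that uses the baseline value, and no mean difference, median difference or ratio with an interval.

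**The concern.** The baseline sample is collected but does not enter any stated comparison of FMT with control. The paired tests use it, but they compare two times within patients, not two arms. If a marker's week-one value is correlated with its baseline, a between-arm test that leaves the baseline out gives away precision in a trial of 30 per arm.

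The estimate is the second gap. The only effect measure with a confidence interval is the relative risk. That suits infectious complications, organ failure and mortality, but it has no meaning for a concentration that is not dichotomised. Read literally, the plan yields a p-value for each marker and no statement of how large the effect could be. Hospital stay has the same reporting gap.

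At stake are the width of the intervals and the chance of detecting an effect on the trial's direct measures of barrier function and inflammation. The binary primary endpoint and the sample size are not affected.

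**Working it through.** **Inputs from the document.** 30 per arm enrolled; a minimum of 24 per arm (Sample size: "we calculated that a minimal sample size of 48 with 24 patients in each group was required"); two-sided 5% level (Statistical analysis). The plan gives no figure for the markers, so there is none to reproduce. The 24 per arm belongs to the binary primary outcome. With 85% against 50% it comes from the unpooled formula, (1.960 + 0.842)² × (0.85×0.15 + 0.50×0.50) / 0.35² = 24.19. It is used here only as a second sample size.

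**Assumed inputs.** Effect 0.6 SD; baseline to week-one correlation r from 0 to 0.7; normal data; equal variance at both times. Low r cannot be ruled out, because patients may enter at different stages of the disease (Inclusion criteria: "Onset of pancreatitis within 2 weeks").

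**Formulas.** With effect d in week-one SDs and n per arm, the standard error is √(2v/n) and the noncentrality is d/√(2v/n). The variance factor v is:

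- week-one value: v = 1, df = 2n − 2
- ANCOVA: v = (1 − r²)(1 + 1/(2n − 4)), df = 2n − 3
- change score, for comparison only: v = 2(1 − r), df = 2n − 2

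**Worked case, n = 30, d = 0.6.** Week-one value: standard error √(2/30) = 0.258, noncentrality 2.32, power 0.628, 95% half-width 0.52 SD. ANCOVA at r = 0.5: v = 0.75 × (1 + 1/56) = 0.763, standard error 0.226, noncentrality 2.66, power 0.744, half-width 0.45 SD.

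**Power and 95% half-width (SD units), 30 per arm, 0.6 SD**

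| r | Week-one t-test | ANCOVA | Change-score t-test |
|---|---|---|---|
| 0 | 63%, 0.52 | 62%, 0.52 | 37%, 0.73 |
| 0.2 | 63%, 0.52 | 64%, 0.51 | 44%, 0.65 |
| 0.3 | 63%, 0.52 | 66%, 0.50 | 49%, 0.61 |
| 0.5 | 63%, 0.52 | 74%, 0.45 | 63%, 0.52 |
| 0.7 | 63%, 0.52 | 89%, 0.37 | 84%, 0.40 |

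By simulation (20,000 trials per cell), the Mann-Whitney test on week-one values has about 60% power at every r. With 24 per arm, the week-one t-test has 53% and ANCOVA 52 / 54 / 56 / 64 / 80% over the same r.

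**Downside at r = 0.** ANCOVA spends one degree of freedom for nothing. The loss is 0.8 points at 0.6 SD with 30 per arm. The largest computed is 1.02 points, at 0.7 SD with 24 per arm (66.06% to 65.04%).

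**Scale.** If a marker is log-normal with log SD 1 (assumed), ANCOVA on raw values has 45 / 45 / 46 / 52 / 64% power. At r up to 0.5 that is below the roughly 60% of the Mann-Whitney test, which is unchanged by taking logs. ANCOVA on the log scale keeps the figures in the table.

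**Validity.** In simulation with no effect, all three tests reject in about 5% of trials (0.047 to 0.053).

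**The case against.** The strongest reply is that the stated test is valid under randomisation, so baseline adjustment is an efficiency preference on secondary endpoints whose benefit depends on a correlation nobody has stated. That stands as a limit on size: at r of 0.2 or less the gain over the week-one test is 1 point or none. It does not remove the point, because the adjustment uses data already collected, the downside is about 1 point, and the missing estimate is missing at any r.

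It can also be said that the relative risk sentence was meant only for the binary outcomes, and that reported means and SDs let a reader derive a difference. The first is a fair reading, but it leaves no interval at all for the continuous endpoints. The second fails where medians and ranges are reported, and it never gives a baseline-adjusted difference.

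A reader might go further and infer that the plan leaves week-one value or change open, so that significance often turns on the choice. The documents do not support that strongly. Neither Secondary endpoints nor Statistical analysis mentions change scores, and the plain reading is week-one values between arms and before-after tests within arms. If change scores were used, the two tests would disagree in about a third of trials at 0.6 SD, but only in 7 to 9% at no effect and 0.4 to 10% at 1.2 SD. These figures also move with the equal-variance assumption. The comparison of ANCOVA with the week-one test depends on r but not on the baseline SD.

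**Conclusion.** The point holds as a matter of precision and reporting. The plan's between-arm test for the four markers is unadjusted despite a baseline sample from every patient, and its only effect measure with an interval cannot be applied to them. At 30 per arm and 0.6 SD, ANCOVA changes power by −1, +1, +3, +12 and +26 points at r = 0, 0.2, 0.3, 0.5 and 0.7, and narrows the half-width from 0.52 SD to 0.45 SD at r = 0.5 and 0.37 SD at r = 0.7. The correlation, effect size and distribution are assumptions, so the gain may be small.

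It should not be read as saying that the marker tests are biased, that their type I error is inflated, or that the primary result is in doubt. Nor do the documents suggest that an analysis was chosen after seeing the results.

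**What to change.** In Statistical analysis:

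1. For each of DAO, endotoxin, CRP and PCT, specify ANCOVA of the week-one value on arm and baseline value. Name the scale (raw or log) for each marker before unblinding. Report the adjusted mean difference, or the FMT/control geometric mean ratio if logged, with 95% CI.
2. Restrict relative risks to binary outcomes.
3. As reporting detail, give hospital stay a between-arm difference with 95% CI (mean difference with the t-test, Hodges-Lehmann difference with the Mann-Whitney test), and label the paired tests as within-arm description.

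The cost is wording; no new data are needed. The scale can be fixed blind, because under Randomization and masking "The randomization key was revealed to researchers when all participants completed the 6-month follow-up and data analysis was completed". The section is written in the past tense. If the analysis has already been done, add the ANCOVA and label it post hoc: it still improves precision, but it cannot undo an analytic choice already made.

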### **Microbiomics analysis**

Fecal samples were longitudinally collected from patients at baseline before first FMT, one weeks and two weeks after first FMT. The fresh feces were collected in sterile cryopreservation tube by the nurses and kept at -20 °C immediately. Then, the feces were transferred within 6 hour after a bowel movement, and were stored at -80 °C until DNA extraction.

Bacterial DNA was extracted from fecal samples using the E.Z.N.A. Soil DNA Kit (Omega Bio-Tek, Norcross, GA, USA) according to the manufacturer's instructions. The final DNA concentration and purification were determined by NanoDrop 2000 UV-vis spectrophotometer (Thermo Scientific, Wilmington, USA), and DNA quality was checked by 1% agarose gel electrophoresis. The V3-V4 hypervariable regions of the bacteria 16S rRNA gene were amplified with primers 338F (5'-ACTCCTACGGGAGGCAGCAG-3') and 806R (5'-GGACTACHVGGGTWTCTAAT-3') by thermocycler PCR system (GeneAmp 9700, ABI, USA). The PCR reactions were conducted using the following program: 3 min of denaturation at 95°C, 27 cycles of 30 s at 95°C, 30 s for annealing at 55°C, and 45 s for elongation at 72°C, and a final extension at 72°C for 10 min. PCR reactions were performed in triplicate 20 µL mixture containing 4 µL of 5 × FastPfu Buffer, 2 µL of 2.5 mM dNTPs, 0.8 µL of each primer (5 µM), 0.4 µL of FastPfu Polymerase and 10 ng of template DNA. The resulted PCR products were extracted from a 2% agarose gel and further purified using the AxyPrep DNA Gel Extraction Kit (Axygen Biosciences, Union City, CA, USA) and qualified using QuantiFluro-ST (Promega, USA).

Purified amplicons were pooled in equimolar and paired-end sequenced (2×300) on an Illumina MiSeq platform (Illumina, San Diego, USA). The raw reads were deposited into the NCBI Sequence Read Archive (SRA) database (Accession Number: SRP). The raw reads were demultiplexed and quality-filtered by Trimmomatic and merged by FLASH software. The high-quality sequences were assigned to samples according to barcodes. Operational taxonomic units (OTUs) were clustered with 97% similarity cutoff using UPARSE (version 7.1, <http://drive5.com/uparse/>) and chimeric sequences were identified and removed using UCHIME. The taxonomy of each 16S rRNA gene sequencing was analyzed by RDP Classifier algorithm (<http://rdp.cme.msu.edu/>) against the Siva (SSU123) 16S rRNA database using confidence threshold of 70%.

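### Secondary outcomes (8 to 13 comparisons) share one unadjusted P<0.05 rule with no exploratory label, and the microbiota aim has no stated test or false-discovery control

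*Combined protocol and SAP*

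**What the plan says.** The combined protocol and SAP has one statistical section, Statistical analysis. It names t, Mann-Whitney, chi-square, Fisher's exact and paired tests, promises relative risks with 95% confidence intervals, and then gives a 0.05 threshold: "for primary outcomes and secondary outcomes. A two-tailed P value". The quoted words are the end of the sentence on relative risks and the start of the separate sentence on the threshold. Nothing limits the threshold to one endpoint, orders the endpoints, adjusts for their number or marks any of them as exploratory.

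Primary Endpoint defines a single endpoint at one time point, and Sample size is built on it. Secondary endpoints lists infection, organ failure, gut barrier function, inflammation, length of stay and death. It names two barrier markers (DAO, endotoxin) and two inflammatory markers (CRP, PCT). Of infection it says: "Infectious complications included IPN, infected ascites, bacteremia, pneumonia, urinary tract infection".

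The end of the Introduction makes infectious complications and gut microbiota aims of the trial alongside gastrointestinal dysfunction. Stool is collected at baseline, one week and two weeks. Microbiomics analysis covers laboratory work and bioinformatics ("Operational taxonomic units (OTUs) were clustered with 97% similarity cutoff") and stops at taxonomy assignment. It names no statistical comparison.

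**The concern.** Two of the three stated aims rest on results for which the only decision rule is an unadjusted 0.05 threshold. When that threshold is used on many comparisons, some will cross it by chance even if the treatment does nothing, and the plan gives the reader no way to discount them. The Introduction says no randomised trial of this treatment in acute pancreatitis has been published, so a secondary result called significant could be read as first evidence.

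The microbiota data raise the same problem on a larger scale. They come as a table of many taxa at three times, and the plan offers no rule for them other than the general one.

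**Working it through.** **The plan's own figure.** The documents give no familywise error rate. The one figure tied to the 0.05 level is the sample size: "a minimal sample size of 48 with 24 patients in each group was required", "using a type I error of 0.05 and a type II error of 0.20 (80% power". Reading the 85% and 50% in that section as recovery rates (the text calls them power), the unpooled two-proportion formula at two-sided 0.05 and 80% power gives

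n per arm = (1.960 + 0.842)² × (0.85 × 0.15 + 0.50 × 0.50) / 0.35² = 24.19,

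which is 24 to the nearest whole number. This reproduces the plan and shows that the 0.05 was budgeted for one test of the primary endpoint. It has no further bearing on this point.

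**Counting the secondary comparisons** (from Secondary endpoints):
- Listed endpoints and named markers only: any infection, organ failure, DAO, endotoxin, CRP, PCT, hospital stay, mortality = 8.
- Adding the five infection types: 8 + 5 = 13.
- Persistent organ failure is also defined and would make 14. Before/after paired tests of the blood markers and the 6-month follow-up outcomes could add more, but the plan does not list them as tests, so they are not counted.

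**Chance of at least one false positive**, all null hypotheses true, each test at 0.05, independent: 1 − 0.95^k.

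| k | Chance of at least one | Expected number (0.05k) |
|---|---|---|
| 6 (infection only) | 26.5% | 0.30 |
| 8 | 33.7% | 0.40 |
| 13 | 48.7% | 0.65 |
| 14 | 51.2% | 0.70 |

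**Allowing for correlation.** The outcomes cannot be independent: any infection is the union of the five types. Simulating normal test statistics with a common correlation (200,000 draws; the correlations are assumptions) gives:

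| k | r = 0.3 | r = 0.5 | r = 0.7 |
|---|---|---|---|
| 6 | 24% | 21% | 16% |
| 13 | 42% | 33% | 24% |

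**Allowing for the actual test size.** At 30 per arm, with event rates assumed between 5% and 50%, Fisher's exact test has a true size of 0.0015 to 0.027. Over six independent tests that is 0.9% to 15%. The uncorrected chi-square test has a size of 0.028 to 0.054, or 16% to 29% over six.

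**Microbiota.** The plan gives neither a taxon count nor a per-taxon test, so both are assumed here. Expected false positives per between-arm comparison at 0.05 are 0.05 × 50 = 2.5 and 0.05 × 500 = 25. With independent taxa, the chance of at least one is 1 − 0.95^50 = 92% for 50 taxa and 99.4% for 100.

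**The case against.** The confirmatory claim is protected. There is one primary endpoint at one time, the sample size is built on it, and everything else is already called secondary. Many readers treat secondary P values as descriptive without being told. Relative risks with intervals are already promised for secondary outcomes. The five infection types are given as the content of one endpoint, not as five further endpoints, so 8 is a fair count. The outcomes are correlated, and where Fisher's test is used its real error rate is well below 0.05.

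All of that stands, and it limits the size of the problem without removing it. Calling an endpoint secondary does not say that its P values are descriptive when the same section sets a significance threshold without restriction. Relative risks do not cover the four blood markers or hospital stay.

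A reader might go further in three ways that the documents do not support:
- *False infection findings are close to certain.* Six infection tests give about 27% at the nominal level with independence, and less with correlation or Fisher's test.
- *The plan applies the threshold to every taxon.* Statistical analysis never mentions taxa or microbiota. The accurate criticism is that a stated aim has no stated method, so the general rule is the only one available. Near-certainty arises only if per-taxon testing of many taxa is assumed.
- *The primary endpoint is fragile, so secondary results will carry the conclusion.* Nothing in the documents shows this; it would be speculation about later reporting.

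**Conclusion.** The point holds in a moderate form. The plan's rule lets 8 to 13 secondary comparisons be called significant at 0.05 with no multiplicity control and no exploratory label. Under a complete null, the chance of at least one false positive is 34% to 49% with independent tests. For 13 tests it is about 24% to 42% at common correlations of 0.7 to 0.3, and lower again where Fisher's test governs rare events. These figures rest on the count chosen, the assumed correlation and each test running at its nominal level. The single primary test at 0.05 is not inflated.

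For the microbiota, the finding is a missing method. The 2.5 to 25 expected false positives are conditional on an assumed 50 to 500 taxa and an assumed per-taxon test, and show what would follow if the general rule were used by default.

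**What to change.** In Statistical analysis:
- State that the phrase statistically significant at the two-sided 0.05 level is used for the primary endpoint only.
- Report secondary outcomes as estimates with 95% confidence intervals: the relative risks already promised for binary outcomes, and between-arm differences for the blood markers and hospital stay. Label them exploratory. Report mortality and safety in full whatever the P value.
- If the sponsor wants to claim a particular secondary effect, prespecify a hierarchy or a Holm procedure for it.

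In Microbiomics analysis, or by cross-reference to it:
- Name one global between-arm test (PERMANOVA is one option), with its distance measure and the time point at which it is applied.
- For individual taxa, control the false discovery rate, for example by Benjamini-Hochberg at 5%, across all taxa, taxonomic levels and time points tested. Control within each level alone would leave multiplicity across levels and times open.
- Name the software if SPSS, the only package listed for the statistical analysis, cannot do this.

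No procedure, visit, sample or patient number changes. The cost is fewer results called significant, and some extra analysis work to specify and run the microbiota methods.
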